7.5. Relationship to study product or study procedure

A determination will be made in relation to the likely relationship (if any) between an adverse event and the study product or study procedure, as applicable. A causal relationship is present if a determination is made that there is a reasonable possibility that the adverse event may have been caused by the study product or study procedure.

Adverse events will subsequently be classified according to the safety reporting flowchart in the NHMRC safety monitoring and reporting guidelines. Any serious adverse event occurring during the study period (beginning with informed consent) and for at least 28 days after the last dose of study product must be immediately reported according to HREC guidelines, no later than 24 hours after learning of a serious adverse event. All SAEs will be immediately (within 24 hours) reported to the medical monitor and the principal investigator. The medical monitor will make a judgment in relation to whether the SAE is likely related to the study product, and whether this outcome affects the potential safety of other participants in the study.

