1.1.4. Expected duration of study

This study is expected to run for a total of 2.5 years from recruitment to the completion of the last participant's last visit. The length of treatment for an individual participant, including all follow-up visits, is six months.

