3.1. Interventions

3.1.1. Omega-3 oral supplements

Treatment arm: triglyceride form omega-3 oral supplement (Caruso's Natural Health Triple Strength fish oil). Each 1500mg capsule contains active ingredients of 540mg Eicosapentaenoic Acid (EPA) and 360mg Docosahexaenoic Acid (DHA).

Participants will be asked to consume two capsules per day; the total active dose of omega-3 triglycerides consumed will be 1080mg EPA +720mg DHA per day for 180 days.

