7.1. Summary

Safety measures will include:

- Adverse events query (Visits 1, 3, 4 and 6)
- Habitual distance visual acuity, BCVA (Visits 1, 3, 4 and 6)
- Intraocular pressure, IOP (Visits 1 and 6)
- Retinal imaging and ocular fundus examination (Visits 1 and 6)
- Basic blood tests (Visits 2 and 5)

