7.3. Adverse events (AEs)

7.3.1. Assessments and documentations of adverse events

All AEs and SAEs will be immediately (within 24 hours) reported to the Principal Investigator by the research team member.

At Visit 1, after informed consent and before the initial study products are administered, all pretreatment adverse events will be documented (e.g., allergic response to topical anaesthetic). Conditions that are present at screening and do not deteriorate will not be considered adverse events.

After the study product supply, all treatment-emergent post-treatment adverse events will be documented. Abnormal laboratory values will not be considered adverse events unless deemed clinically significant by the medical monitor, and documented as such.

If adverse events occur, the first concern will always be the safety of the study participants. All adverse events, including severity, action taken and likely relationship to the study product will be documented throughout the study.

At each visit, the co-investigator or principal investigator will begin the examination by querying for adverse events by asking each participant a general, non-directed question such as "How have you been feeling since the last visit?" Directed questioning and examination will then be carried out as appropriate.

The description of each AE recorded will include:

- A description of the AE;
- The onset date, duration, date of resolution;
- Severity (assessed as per section 7.4;
- Seriousness (i.e., is it an SAE?);

nPROOFS1-v1.2 [01-July-2018] Page 23 of 53

- Actions taken;
- The outcome;
- The likelihood of the relationship of the AE to the study treatment (Unrelated, Possible, Probable, Definite).

For each adverse event reported, the number and percent of participants affected will be tabulated. Separate adverse event tables will be generated for pre-treatment AEs and post-treatment AEs. All adverse events will be presented in the listings. Other safety variables, including biomicroscopy findings, BCVA, IOP, retinal fundus photograph and blood test results will be analysed.

DEFINITIONS:

• An adverse event is **any** untoward medical occurrence in a participant or clinical investigation of participant administered a pharmaceutical product. It does not necessarily have a causal relationship with treatment.

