7.3.2. Serious adverse events (SAEs)

- A serious adverse event is any adverse event that results in any of the following outcomes:
 - o death
 - o a life-threatening adverse event
 - o inpatient hospitalisation or prolongation of existing hospitalisation (for any reason)
 - o a persistent or significant disability/incapacity
 - o a congenital anomaly/birth defect
 - a diagnosis of cancer
 - o any abortion (spontaneous or non-spontaneous)

• A Suspected Unexpected Serious Adverse Reaction (SUSAR) is any SAE that is both suspected to be related to the study treatment and is unexpected (i.e., not consistent with applicable product information)

Important medical events that may not result in death, be life-threatening, or require hospitalisation may be considered a serious adverse event when, based upon appropriate medical judgment, they may jeopardise the participant or may require medical or surgical intervention to prevent one of the outcomes listed in this definition. (See below for procedures for reporting a serious adverse event.)

Pre-planned surgeries or procedures for pre-existing, known medical conditions, for which a participant requires hospitalisation are not reportable as a serious adverse event. Any pre-planned surgery or procedure should be clearly documented in the site source documents by the medically qualified investigator at the time of the participant's entry into the study. If it has not been documented at the time of the patient's entry into the study, then it should be documented as a serious adverse event and reported as such.

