- Quantitative sudomotor axonal reflex testing
- Nerve conduction studies
- Nerve excitability tests
- Blood samples

Visit 3 (23 to 37 days, The University of Melbourne, 1 hour)

The following procedures will be performed at Visit 3:

- Adverse event assessment
- Diet questioning
- Medical and ophthalmic histories
- Habitual/best corrected visual acuity
- Slit lamp examination

Visit 4 (76 to 104 days, The University of Melbourne, 1 hour)

The following procedures will be performed at Visit 4:

- Adverse event assessment
- Diet questioning
- Medical and ophthalmic histories

nPROOFS1-v1.2 [01-July-2018] Page 31 of 53

- OSDI questionnaire
- Habitual/best corrected visual acuity
- Non-contact aesthesiometry
- Slit-lamp examination
- TBUT
- Ocular surface staining (Oxford scale)
- Corneal confocal microscopy (with anaesthesia)
- Dispense of masked study product

Visit 5 (156 to 204 days, St Vincent's Hospital Melbourne, 2 hours)

The following procedures will be performed at Visit 5:

- Brief medical history (including related neuropathy symptoms)
- Michigan Diabetic Neuropathy Score
- Cutaneous silent period testing
- Quantitative sudomotor axonal reflex testing
- Nerve conduction studies
- Nerve excitability tests
- Blood samples

Visit 6 (156 to 204 days, The University of Melbourne, 2 hours) or Early exit

- Adverse event assessment
- Medical and ophthalmic histories
- Diet questioning
- Urine pregnancy test (for females of childbearing potential only)
- Habitual/ best corrected visual acuity
- MNSI questionnaire
- OSDI questionnaire
- EQ-5D-5L questionnaire
- iMTA questionnaire
- Tear osmolarity
- Basal (non-stimulated) tear collection
- Non-contact aesthesiometry
- Slit lamp examination
- Anterior chamber angle assessment
- TBUT
- Ocular surface staining (Oxford scale)
- IOP (with anaesthesia and fluorescein using a Goldmann tonometer)
- Corneal confocal microscopy (with anaesthesia)
- Dilated fundus examination (with mydriatic eye drops) and non-invasive retinal imaging
- Pin-prick blood sample
- Collection of unused study supplements

Unscheduled visits

Unscheduled visits may be arranged, as necessary, to ensure the safety and well-being of participants during the study. Source documentation should be completed for all parameters

nPROOFS1-v1.2 [01-July-2018] Page 32 of 53

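### Serious adverse events are reportable to at least 28 days after the last dose, but no adverse-event query is scheduled that late after a full course, and the text conflicts on whether Visit 5 has one

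*Combined protocol and SAP*

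**What the plan says.** **Reporting period.** Section 7.5 runs the serious-event period from informed consent and "for at least 28 days after the last dose of study product must be immediately reported according to HREC guidelines". The clock for the duty is "no later than 24 hours after learning of a serious adverse event".

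**Dosing and follow-up.** Section 3.1.1 gives the active dose as "1080mg EPA +720mg DHA per day for 180 days", and section 10.4 starts it on the day of Visit 2 (Day 1). Section 1.1.4 states: "The length of treatment for an individual participant, including all follow-up visits, is six months". Visits 5 and 6 have the same window in section 10.4, Day 156 to 204. The Visit 6 list includes an adverse-event assessment and "Collection of unused study supplements". Section 10.5 asks only that the hospital visits fall within four weeks of the initial and final visits.

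**Adverse-event queries.** The safety summary in section 7.1 lists "Adverse events query (Visits 1, 3, 4 and 6"). The Visit 5 list in section 10.4 contains a brief medical history but no adverse-event assessment. Section 7.3.1 says: "At each visit, the co-investigator or principal investigator will begin the examination by querying for adverse events".

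**After exit.** Section 7.6 follows up events marked as ongoing at the exit visit. Section 10.4 allows unscheduled visits as needed, and section 10.5 encourages participants to contact the principal investigator at any time. No other contact after exit is described.

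**The concern.** A duty that begins when the team learns of an event is only as complete as its means of learning. The protocol names a period that outlasts its last planned question and sets no later visit, call or message. A new serious event after Visit 6 becomes known only if the participant or a treating clinician volunteers it.

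The conflict over Visit 5 adds to this. That visit holds the end-of-treatment bloods, the electrical-stimulation tests and the sweat test, and section 7.5 covers events related to a study procedure as well as to the product. If Visit 5 comes after Visit 6 and has no query, nothing scheduled asks about what followed those procedures.

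Safety is Aim 3 of the SAP. Supplementary Table S3 reports participants with at least one serious event as 0 of 21 on omega-3 and 1 of 22 on placebo, without stating the period over which events were sought. With counts this small, one unasked event would change the row, and a reader of section 7.5 may assume that the 28 days were actively covered.

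**Working it through.** **Inputs**
- Dosing of 180 days (section 3.1.1), first dose on Day 1 (section 10.4). The SAP (section 10) counts days as visit date minus start date, so the start is Day 0.
- Reporting period to at least 28 days after the last dose (section 7.5).
- Visits 5 and 6 at Day 180 ± 24 (section 4), not more than four weeks apart (section 10.5).

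**Step 1: reproduce the stated window.** 180 − 24 = 156 and 180 + 24 = 204, matching section 10.4 and the SAP's visit-window table.

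**Step 2: end of the 28 days after a completed course**
- Start = Day 1: last dose Day 180; 180 + 28 = Day 208.
- Start = Day 0: last dose Day 179; 179 + 28 = Day 207.

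**Step 3: coverage by the last listed query (Visit 6)**

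| Visit 6 on | Days covered of 28, start = Day 1 | Days covered of 28, start = Day 0 |
|---|---|---|
| Day 156 | 0 | 0 |
| Day 180 | 0 | 180 − 179 = 1 |
| Day 204 | 204 − 180 = 24 | 204 − 179 = 25 |

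The smallest uncovered tail is therefore 208 − 204 = 4 days, or 207 − 204 = 3 days. If a participant keeps taking capsules until they are collected at Visit 6, all 28 days lie after Visit 6, ending between 156 + 28 = Day 184 and 204 + 28 = Day 232.

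**Step 4: order of Visits 5 and 6.** The window holds 204 − 156 + 1 = 49 days. For a gap of d days there are 49 − d pairs with Visit 5 after Visit 6. Summing over d = 1 to 28 gives 28 × 49 − (28 × 29)/2 = 1,372 − 406 = 966. The same number have Visit 5 first, and 49 have both on one day: 966 + 966 + 49 = 1,981 permitted pairs. These count what the windows allow; they are not probabilities.

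**Step 5: does any scheduled visit reach day 28?** Take the last dose as the earlier of Visit 6 and Day 180. Visit 6 reaches day 28 in 0 of the 1,981 pairs. Visit 5 reaches it in 21: Visit 6 on Day 156 to 176 (176 − 156 + 1 = 21 days) with Visit 5 exactly 28 days later. In those pairs dosing stopped before Day 180, and the visit that lands on day 28 is the one with no listed query.

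**Step 6: the Visit 5 texts side by side.** Sections 7.1 and 10.4 leave Visit 5 out; section 7.3.1 includes every visit. Sections 11.1.5 and 11.1.14 use the same every-visit wording for visual acuity and slit-lamp examination, which are done only at the university visits, so section 7.3.1 may have been meant loosely too. The schedule table in section 4 has an adverse-event row, but its visit marks did not survive in the text available for this review, so it cannot settle the point.

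**The case against.** The strongest reply is that section 7.5 creates a duty to report, not a promise to ask. It starts when someone learns of an event and refers to ethics committee guidelines that are not in the documents. A reader might infer that the protocol promises active capture to day 28 and breaks that promise; the text does not say so. This stands. The gap is the absence of a planned route to the knowledge that the duty depends on.

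Other parts of the reply also stand:
- A reader might conclude that the 28 days are observed for nobody. That is too strong: a late Visit 6 covers up to 24 or 25 of them.
- A reader might take it as settled that Visit 5 has no adverse-event query. The documents contradict each other, and the brief medical history could bring events to light.
- Visit 5 after exit is permitted but not shown to be planned. Section 10.5 treats the university visit as the final one and has Visit 5 booked at Visit 4.
- Six months in section 1.1.4 is a rounded duration, and section 7.6 does continue follow-up of ongoing events.
- A reader might also see a gap for pregnancies, since section 7.3.2 lists "any abortion (spontaneous or non-spontaneous") and congenital anomaly as serious outcomes while section 2.4.4 exits a participant who becomes pregnant. But section 2.4.4 also provides follow-up directed by the principal investigator and notice to the GP. No gap is shown, and pregnancy forms no part of this point.

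Unscheduled visits and participant-initiated contact do not answer the main point: both depend on someone coming forward.

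**Conclusion.** The point holds as a cheap improvement to safety ascertainment. For a completed 180-day course, the reporting period outlasts the last listed adverse-event query by at least 3 to 4 days, and by the whole 28 days when Visit 6 falls on or before the last dose. Separately, sections 7.1 and 10.4 conflict with section 7.3.1 on Visit 5, and the shared window allows that visit to come after exit.

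This rests on dosing stopping at 180 days or at Visit 6 if earlier, on visits staying within their windows, and on no contact being scheduled outside the documents. How often Visit 5 followed Visit 6, and whether any event was missed, cannot be determined from the documents. Nothing here bears on the primary CNFL analysis.

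**What to change.** **In the protocol**
- Add one phone or email contact by existing study staff at 28 days or more after the last dose, for completers and early exits alike, asking about new serious events. Amend section 1.1.4 to include it.
- Add the adverse-event query to Visit 5, so that sections 7.1 and 10.4 agree with section 7.3.1.

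The cost is about 43 to 50 short calls (43 was the reduced target, 50 the planned number), one question at Visit 5 and some wording. No visit is added. The downside is nominally about four more weeks of participation.

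**For this trial now.** The SAP dates the last participant's last visit to March 10, 2020, so a contact cannot be added prospectively. The report can state the actual adverse-event ascertainment window, describe the post-exit period as passively reported, and say whether Visit 5 was queried. A footnote to Table S3 and a sentence in the methods would be enough.

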7.6. Procedures for reporting adverse events

All adverse events will be recorded on the appropriate sections in REDCap and the principal investigator will be informed within 24 hours. Any adverse event that is marked as 'ongoing' at the exit visit will be followed-up, as appropriate.

All SUSARs will be reported to the Institution (University of Melbourne Human Research Ethics Committee) and the Therapeutic Goods Administration (TGA) as soon as possible, and no later than seven calendar days for fatal or life threatening SUSARs, and 15 calendar days for all other SUSARs.

An annual safety report will be generated by the Principal Investigator and provided to the governing institutional human research ethics committee (HREC), as required by the HREC, local regulations, and the governing health authorities to provide a clear summary of the evolving safety profile of the trial. The annual safety report will include

- o a brief description and analysis of new and relevant findings (as permissible);
- o a brief discussion of the implications of the safety data to the trial's risk-benefit ratio;
- o a description of any measures taken or proposed to minimise risk

The Principal Investigator will complete the annual review and provide the HREC and investigators with updates/addenda to the Investigator's Brochure, should new or relevant information become available.

The Principal Investigator will notify the Institution, the TGA and investigators (co-investigators and associate investigators) of all significant safety issues, amendments, temporary halt or early termination of a trial. Significant safety issues that meet the definition of an urgent safety measure should be notified within 72 hours, and all other significant safety issues should be notified within 15 calendar days

Definitions:

Significant safety issues are issues that adversely affect the safety of participants or materially impact on the continued ethical acceptability or conduct of the trial. These may require an urgent safety measure, an amendment, a temporary halt or an early termination of a trial.

Urgent Safety Measures (USMs) are significant safety issues where sponsors or trial investigators act immediately to protect participants from an immediate hazard to their health and safety.

7.7. Administrative items

This study protocol is to be conducted in accordance with the applicable Good Clinical Practice (GCP) regulations and guidelines (e.g., the International Conference on Harmonisation (ICH) Guideline on GCP).

All safety monitoring and reporting will be conducted according to the NHMRC 'Safety monitoring and reporting in clinical trials involving therapeutic goods" handbook.

8. Statistical Analysis

8.1. Statistical methods

A separate statistical analysis plan will be developed and finalised prior to study unmasking.

Data relating to participant demographics and baseline clinical characteristics will be analysed with a repeated measures model or ordered logistic regression model, as appropriate. For the primary outcome, analyses will be performed on data from right eyes. For slit lamp examination, analyses will be performed on the average of data from both eyes. For neurophysiological data, analyses will be performed on data from one limb only.

